4.1.4 Drug assignment and administration of doses for each patient

In this trial a dose of 300 mg of BI 655130 (SPESOLIMAB) will be administered during study visit as subcutaneous injection in the abdomen, in accordance with local standard

procedure and as described in “BI 655130 Solution for Injection 150 mg/mL s.c. Instructions for Handling and Use”

every 4 weeks for patients starting from visit M1 until EOT visit for patients who responded to treatment with study drug in previous trials or gained response after i.v. re-induction period. The concentration of the application solution will be 150 mg/ml.

Injection site should not be close to a vein and it should avoid sites where the skin is tender, bruised, erythematous, or indurated, and should be alternated to other areas for subsequent doses.

Detailed instructions for Handling and Use of s.c. injection are provided in the ISF.

Patients have to be closely monitored for local or systemic hypersensitivity reactions for 1 hour following s.c. study drug administration. Subcutaneous administration of biologic agents involves the risk of local (injection site) or systemic hypersensitivity reactions. Therefore, patients should be closely monitored for signs and symptoms of injection site or systemic hypersensitivity reactions following study drug administration. Study personnel should observe the injection site for signs of redness, swelling or hardness. They should also ask subjects about itching, dizziness or shortness of breath. Patients should be advised that if they experience redness, swelling or other changes at the injection site, they should notify site personnel. They should further be advised that if they experience itching all over or a feeling of being swollen, dizzy or short of breath, they should seek emergency medical attention immediately and notify site personnel.

1200mg BI 655130 (SPESOLIMAB) i.v. q4w administration for 12 weeks will be used for patients assigned to i.v. re-induction.

Single 1200 mg BI 655130 (SPESOLIMAB) i.v. administration will be used as disease flare treatment. Intravenous infusion including observational time for possible infusion reactions will last approximately 2.5 hours. The i.v. treatment will be followed by intensified maintenance treatment with 600mg BI 655130 (SPESOLIMAB) q6w.

Detailed instructions for the preparation of the i.v. infusion solution, the volume to be administered and the infusion rate are provided in the ISF.

In case of safety concerns, e.g., due to infusion reactions, it is in the discretion of the investigator or his/her designee to adapt the infusion scheme (cf. [Section 4.2.1](#) for handling of infusion reactions). Detailed instructions for handling of infusion reactions are also provided in the ISF.

The administration of the trial medication intravenously on all applicable study days will be done under supervision of the investigating physician or a designee at the site. If available, a pharmacist should prepare the study medication. The four eye principle (two-person rule) should be applied for preparation (e.g. choosing the correct vials with the correct medication number) and administration of trial medication.

Dose modifications or adjustments are not permitted. In exceptional cases of missed or delayed visits, if any of these visits has to be rescheduled, the date of subsequent visit should be calculated from Day 1 of maintenance treatment or if the patient is on flare treatment from the first s.c. drug administration after the last disease flare. There should be at least 14 days between two consecutive study drug administrations.

4.1.5 Blinding and procedures for unblinding

4.1.5.1 Blinding

This is an open label, single arm trial; therefore no blinding will be necessary. In this open-label trial, treatment allocation will not be concealed throughout the trial.

With regard to the blind of the parent study (1368-0005 part I), patients and investigators will remain blinded with regard to the original randomised treatment assignments until after the final database lock for the initial induction trial has been performed.

4.1.5.2 Unblinding and breaking the code

Not applicable.

4.1.6 Packaging, labelling, and re-supply

The investigational products will be provided by BI or a designated CRO. They will be packaged and labelled in accordance with the principles of Good Manufacturing Practice (GMP). Re-supply to the sites will be managed via an IRT system, which will also monitor expiry dates of supplies available at the sites.

For details of packaging and the description of the label, refer to the ISF.

4.1.7 Storage conditions

Drug supplies will be kept in their original packaging and in a secure limited access storage area according to the recommended storage conditions on the medication label. A temperature log must be maintained for documentation

If the storage conditions are found to be outside the specified range, the local clinical monitor (as provided in the list of contacts) must be contacted immediately. Refer to ISF. Trial medication must be securely stored, e.g. in a locked refrigerator at the site or at a pharmacy. The medication may only be dispensed to trial patients according to the Clinical Trial Protocol (CTP) by authorized personnel as documented in the trial staff list. Trial medication will be prepared for infusion just prior to infusion, for further details please see preparation instructions in the ISF.

4.1.8 Drug accountability

The investigator/pharmacist /investigational drug storage manager will receive the investigational drugs delivered by the sponsor when the following requirements are fulfilled:

- Approval of the clinical trial protocol by the IRB/ethics committee ,
- Availability of a signed and dated clinical trial contract between the sponsor and the investigational site,
- Approval/notification of the regulatory authority, e.g. competent authority,
- Availability of the curriculum vitae of the Principal Investigator,
- Availability of a signed and dated clinical trial protocol,

Proprietary confidential information © 2022 Boehringer Ingelheim International GmbH or one or more of its affiliated companies

- Availability of the proof of a medical license for the Principal Investigator (if applicable),
- Availability of FDA Form 1572 (applicable for US).

Investigational drugs are not allowed to be used outside the context of this protocol. They must not be forwarded to other physicians or clinics.

The investigator/pharmacist/ investigational drug storage manager must maintain records of the product's delivery to the trial site, the inventory at the site, the use by each patient, and the return to the sponsor or warehouse/drug distribution centre or alternative disposal of unused products. If applicable, the sponsor or warehouse/drug distribution centre will maintain records of the disposal.

These records will include dates, quantities, batch/serial numbers, expiry ('use- by') dates, and the unique code numbers assigned to the investigational product and trial patients. The investigator/pharmacist/ investigational drug storage manager will maintain records that document adequately that the patients were provided the doses specified by the CTP and reconcile all investigational products received from the sponsor. At the time of return to the sponsor or appointed CRO, the investigator/pharmacist / investigational drug storage manager must verify that all unused drug supplies have been returned by the clinical trial patient and that no remaining supplies are in the investigator's possession.

4.2 OTHER TREATMENTS, EMERGENCY PROCEDURES, RESTRICTIONS

4.2.1 Other treatments and emergency procedures

If the patient requires additional medical therapy or dose increase of baseline ulcerative colitis medication (other than BI 655130 (SPESOLIMAB) to treat a disease flare or a reversion to the preceding higher daily steroid dose during tapering of steroids) to treat the underlying ulcerative colitis due to disease worsening (cf. [Table 2.1:1](#) Definition of Study Outcomes), the study drug must be discontinued and patients may receive conventional treatment for active disease. In case of disease flare during maintenance treatment period, patient must be provided with disease flare treatment (single i.v. dose of 1200 mg BI 655130 (SPESOLIMAB) infusion) followed by intensified maintenance treatment with 600mg BI 655130 (SPESOLIMAB) q6w.

In case of undue safety risk for the subject, the subject should discontinue study treatment at the discretion of the investigator. If the subject receives a live virus vaccination during the study, the subject must discontinue study treatment.

Systemic steroids dosed intravenously or orally for less than 24 hours as treatment of infusion or anaphylactic reactions are permitted and do not lead to treatment discontinuation (see [Table 4.2.2: 1](#)).

If mild-to-moderate infusion or anaphylactic reaction had already occurred in the very same patient in the past, pre-treatment with steroids before next IMP administration is permitted as secondary prophylaxis.

Locally administered steroids as e.g. intraarticular, nasal inhalation or intraocular administration are allowed, but their application has to be carefully monitored and reported in CRF (see [Table 4.2.2: 1](#)).

Management of Adverse Events:

Infusion reactions / Systemic hypersensitivity including anaphylactic reaction

In case of infusion reactions / systemic hypersensitivity including anaphylactic reaction emerging during or after infusion / injection(s) of study drug, the investigator should consider in accordance with severity of the reaction and local standard of care to:

- Immediately interrupt the infusion / Stop further injections
- Treat with systemic anti-histamines, intravenous steroids, and in case of a severe allergic reaction (e.g., anaphylactic reaction) epinephrine

Also draw a plasma sample for IgE and ADA as detailed in the Lab Manual (available in ISF). Additionally consider the evaluation of histamine, serum tryptase, and complement components.

In case of infusion reaction / systemic hypersensitivity reaction, based on patient's clinical course and medical judgment, the infusion / injections may be re-initiated in case of mild or moderate infusion reactions / systemic hypersensitivity reactions (according to RCTC grading of "allergic reaction/hypersensitivity" in ISF) at lower speed with gradual increase to complete the infusion (in case of an infusion reaction) as detailed in the Instructions for Preparation and Handling of BI 655130 (SPESOLIMAB) in the Investigator Site File.

In case of anaphylactic reaction based on the criteria discussed in the statement paper from Sampson HA ([Appendix 10.5 R11-4890](#)) suspected to be caused by the trial medication, the investigator should discontinue treatment with study drug (see [Appendix 10.5](#) for criteria of anaphylaxis).

When a non-acute hypersensitivity reaction related to immune complexes (i.e., serum sickness) is suspected, please draw a sample for the laboratory assessment for circulating immune complexes (referring to Lab manual).

Severe infections (according to RCTC grading in [Appendix 10.6](#)), serious infections, opportunistic or mycobacterium tuberculosis infection

Treatment of the infection should be initiated promptly according to local standard of care. No further trial medication should be administered until the active infection is resolved. Treatment with trial medication may be restarted when the patient has recovered according to investigator's assessment.

- Latent TB must be treated according to local guidelines. Patient can continue the treatment.

Malignancies

- In case of occurrence of malignant neoplasm other than appropriately treated basal cell carcinoma or squamous cell carcinoma of the skin or in situ carcinoma of uterine cervix, the investigator should discontinue treatment with study drug. Diagnostics and treatment have to be initiated according to local standard of care.

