The latest list of “Always Serious AEs” can be found in the eDC system. A copy of the latest list of “Always Serious AEs” will be provided upon request. These events should always be reported as SAEs as described above.

Adverse Events of Special Interest (AESIs)

The term AESI relates to any specific AE that has been identified at the project level as being of particular interest or prospective safety monitoring and safety assessment within this trial. AESIs need to be reported to the sponsor’s Pharmacovigilance Department within the same timeframe that applies to SAEs, please see above.

The following are considered as AESIs:

- Systemic hypersensitivity including infusion reaction and anaphylactic reaction

Any suspicion of severe infusion reaction and of any potential cases of anaphylaxis should be defined and assessed using the criteria discussed in the statement paper from Sampson HA ([Appendix 10.5, R11-4890](#)).

Severe infections (according to (according to RCTC grading in Appendix 10.6)

Opportunistic and mycobacterium tuberculosis infections

These include pneumocystis jirovecii, BK virus disease including PVAN, CMV, post-transplant lymphoproliferative disorder (EBV), progressive multifocal leucoencephalopathy, bartonellosis (disseminated only), blastomycosis, toxoplasmosis, coccidioidomycosis, histoplasmosis, aspergillosis (invasive only), candidiasis (invasive or pharyngeal), cryptococcosis, other invasive fungi (mucormycosis (zygomycosis, rhizopus, mucor, lichtheimia), scedosporium/pseudallescheria boydii, fusarium), legionellosis, listeria monocytogenes (invasive only), tuberculosis, nocardiosis, non-tuberculous mycobacterium, salmonellosis (invasive only), HBV reactivation, herpes simplex (invasive only), herpes zoster, strongyloides (hyperinfection syndrome and disseminated forms only), paracoccidioides, penicillium marneffei, sporothrix schenckii, cryptosporidium species

(chronic only), microsporidiosis, leishmaniasis (visceral only), trypanosoma cruzi infection (Chagas' disease) (disseminated only), campylobacteriosis (invasive only), shigellosis (invasive only), vibriosis (invasive due to vibrio vulnificus), HCV progression [[R17-2617](#)]

Hepatic injury

A hepatic injury is defined by the following alterations of hepatic laboratory parameters:

- a. ALT or AST >5x ULN
- b. ALT or AST >3x ULN with the appearance of fatigue, nausea, vomiting, right upper quadrant pain or tenderness, fever, rash, and/or eosinophilia (> 5%)

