10.5 DIAGNOSIS OF ANAPHYLAXIS

Clinical Criteria for diagnosing anaphylaxis [\[R11-4890\]](#)

Anaphylaxis is highly likely when any one of the following 3 criteria are fulfilled
1. Acute onset of an illness (minutes to several hours) with involvement of the skin, mucosal tissue, or both (eg, generalized hives, pruritus or flushing, swollen lips-tongue-uvula)
AND AT LEAST ONE OF THE FOLLOWING
a. Respiratory compromise (eg, dyspnea, wheeze-bronchospasm, stridor, reduced PEF, hypoxemia)
b. Reduced BP or associated symptoms of end-organ dysfunction (eg, hypotonia [collapse], syncope, incontinence)
2. Two or more of the following that occur rapidly after exposure to a likely allergen for that patient (minutes to several hours):
a. Involvement of the skin-mucosal tissue (eg, generalized hives, itch-flush, swollen lips-tongue-uvula)
b. Respiratory compromise (eg, dyspnea, wheeze-bronchospasm, stridor, reduced PEF, hypoxemia)
c. Reduced BP or associated symptoms (eg, hypotonia [collapse], syncope, incontinence)
d. Persistent gastrointestinal symptoms (eg, crampy abdominal pain, vomiting)
3. Reduced BP after exposure to known allergen for that patient (minutes to several hours):
a. Infants and children: low systolic BP (age specific) or greater than 30% decrease in systolic BP*
b. Adults: systolic BP of less than 90 mm Hg or greater than 30% decrease from that person's baseline

PEF, Peak expiratory flow; BP, blood pressure.

*Low systolic blood pressure for children is defined as less than 70 mm Hg from 1 month to 1 year, less than (70 mm Hg + [2 x age]) from 1 to 10 years, and less than 90 mm Hg from 11 to 17 years.

**10.6 SEVERITY OF AE AS DESCRIBED IN THE RHEUMATOLOGY
COMMON TOXICITY CRITERIA ([REDACTED])**

Table 10.6:1 Severity of AE as described in the Rheumatology common Toxicity
Criteria ([REDACTED])

	1 - Mild	2 - Moderate	3 - Severe	4 - Includes Life Threatening
	Asymptomatic, or transient Short duration (< 1 week) No change in life style No medication or OTC	Symptomatic Duration (1–2 weeks) Alter lifestyle occasionally Meds relieve. (may be prescription), Study drug continued	Prolonged symptoms, reversible, major functional impairment Prescription meds/partial relief May be hospitalized<24h Temporary study drug discontinuation, or/and dose reduced	At risk of death Substantial disability, especially if permanent. Multiple meds Hospitalised >24h Study drug discontinued
A.ALLERGIC/IMMUNOLOGIC				

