A1. Allergic reaction/ hypersensitivity (including drug fever)	Transient rash; drug fever < 38° C, transient asymptomatic bronchospasm	Generalized urticaria responsive to meds; or drug fever > 38° C, or reversible bronchospasm	Symptomatic bronchospasm, requiring meds; symptomatic urticaria persisting with meds, allergy related oedema/ angioedema	Anaphylaxis, laryngeal/ pharyngeal edema, requiring resuscitation
A2. Autoimmune reaction	Serologic or other evidence of autoimmune reaction but patient asymptomatic: all organ function normal and no treatment is required (e.g., vitiligo)	Evidence of autoimmune reaction involving a non-essential organ or functions, requiring treatment other than immunosuppressive drugs (e.g., hypothyroidism)	Reversible autoimmune reaction involving function of a major organ or toxicity requiring short term immunosuppressive treatment (e.g., transient colitis or anemia)	Causes major organ dysfunction, or progressive, not reversible, or requires long term administration of high dose immunosuppressive therapy

Table 10.6: 1 Severity of AE as described in the Rheumatology common Toxicity Criteria (██████) (Cont.)

	1 - Mild	2 - Moderate	3 - Severe	4 - Includes Life Threatening
A3. Rhinitis (includes sneezing, nasal stuffiness, post nasal discharge)	Transient, non-prescription meds relieve	Prescription med required, slow	Corticosteroids or other prescription med. with persistent disabling symptoms such as impaired exercise tolerance	NA

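### Protocol 4.2.1 allows steroid cover for a next dose after a mild-to-moderate anaphylactic reaction, while its own stop rule for drug-suspected anaphylaxis has no grade limit

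*Protocol*

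**What the plan says.** Section 4.2.1 of the protocol contains three relevant statements.

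- **Steroids as treatment.** Systemic steroid courses of under 24 hours "as treatment of infusion or anaphylactic reactions are permitted and do not lead to treatment discontinuation".
- **Steroids as prophylaxis.** The next paragraph reads "If mild-to-moderate infusion or anaphylactic reaction had already occurred in the very same patient in the past, pre-treatment with steroids before next IMP administration" and goes on to permit this as secondary prophylaxis.
- **Stop rule.** Under the heading on management of adverse events, when an anaphylactic reaction by the Appendix 10.5 criteria is "suspected to be caused by the trial medication, the investigator should discontinue treatment with study drug". No RCTC grade is attached. The paragraph before it lets infusions or injections restart after mild or moderate infusion or systemic hypersensitivity reactions, and does not name anaphylaxis.

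Other text bears on how a reaction is classified. The treatment list in 4.2.1 reads "in case of a severe allergic reaction (e.g., anaphylactic reaction) epinephrine". Section 5.2.6.1 says "any potential cases of anaphylaxis should be defined and assessed using the criteria discussed in the statement paper", meaning the Appendix 10.5 criteria. In Appendix 10.6, Table 10.6:1, the allergy row (A1) has "Anaphylaxis, laryngeal/ pharyngeal edema, requiring resuscitation" at Grade 4, under a column header that includes "Multiple meds Hospitalised >24h Study drug discontinued". Grade 2 of the same row is "Generalized urticaria responsive to meds; or drug fever > 38° C, or reversible bronchospasm", under a header that has study drug carrying on.

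**The concern.** Pre-treatment ahead of a dose presupposes that the dose is given, and calling it secondary prophylaxis implies that the earlier reaction was to the study drug. Applied to anaphylaxis, this describes a patient whom the stop rule would already have taken off treatment. The protocol does not say which statement prevails. Section 3.3.4.1 sends readers to 4.2.1 for stopping rules tied to specific adverse events, and the risk table in section 1.4 speaks only of considering interruption and treatment. So 4.2.1 is the operative source, and it gives two messages.

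What is at stake is a further dose of a monoclonal antibody after drug-suspected anaphylaxis. Long-term safety is the trial's first objective, and section 1.4 says that the general benefit-risk for patients now on treatment cannot be evaluated.

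**Working it through.** The point rests on wording, so the check is a comparison of texts. The plan gives no figure to reproduce.

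**Step 1. Are both statements current?** Yes. Both stand in the body of version 8.0. The amendment log shows that Global Amendment 2 added the prophylaxis sentence, and the sentence is still there.

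**Step 2. Can the grammar remove the conflict?** There are two readings.
- If mild-to-moderate qualifies both kinds of reaction, the sentence covers mild-to-moderate anaphylactic reactions.
- If it qualifies only infusion reactions, the sentence covers every anaphylactic reaction and the conflict is wider.

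**Step 3. Can the scope remove the conflict?** The two statements fit together if the prophylaxis sentence is confined to reactions that fall short of Appendix 10.5 or are not attributed to the drug. The protocol does not state that limit.

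**Step 4. Can the grading remove the conflict?** Largely. Section 4.2.1 treats anaphylactic reaction as an example of a severe reaction, and row A1 names anaphylaxis only at Grade 4. If every reaction meeting Appendix 10.5 is Grade 4, no mild or moderate anaphylaxis exists and the phrase describes nothing.

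**Step 5. Does any case remain?** Take generalized urticaria that responds to medication, with persistent vomiting, starting rapidly after a dose.

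| Source | Reading of this case | Points to |
|---|---|---|
| Table 10.6:1, row A1, by the skin component | Grade 2 | drug continued (column header) |
| Appendix 10.5, criterion 2, items a (skin-mucosal) and d (gastrointestinal) | anaphylaxis highly likely | discontinuation, if drug-suspected (4.2.1) |
| Table 10.6:1, row A1, by diagnosis | Grade 4, if the resuscitation qualifier is read as applying to oedema only | drug discontinued (column header) |

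Row A1 has no gastrointestinal term that would raise the grade. The Grade 4 entry can also be read as requiring resuscitation for anaphylaxis too, which would leave this case out of Grade 4. A site could therefore reach Grade 2 and read the prophylaxis sentence as applicable. The bronchospasm route is narrower, because symptomatic bronchospasm needing medication is already Grade 3.

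**Step 6. Does the primary endpoint change?** No. SAP section 7.8.1 counts patients with an event, and an affected patient's time at risk ends at event onset. The reaction is itself an adverse event, so a later dose cannot change that patient's contribution to the any-TEAE rate in that period.

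**The case against.** The best defence is that a concomitant-medication permission does not compete with a stop rule. The prophylaxis sentence says which steroid use is acceptable if a next dose is given. Where the stop rule applies there is no next dose, and a site can obey both. This largely stands: the sentence is not an instruction to re-dose. What remains is that it names anaphylactic reactions among those after which a next dose is foreseen, and it does not point to the stop rule.

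The second argument is that a reaction diagnosed by Appendix 10.5 is anaphylaxis and hence Grade 4, so the Grade 2 case exists only if a site grades by one component. That is the more natural reading and makes the overlap arguable. It does not close the case, given the Grade 2 header and the ambiguous resuscitation qualifier. If it did, the phrase would have no content and could be deleted without loss.

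Third, there are safeguards:
- AESI reporting within 24 hours (5.2.6.1, 5.2.6.2);
- agreement with the sponsor's clinical monitor on pre-medication for further injections (5.2.2);
- discontinuation for undue safety risk (4.2.1) or when continuing is not in the patient's best interest (3.3.4.1);
- individual benefit-risk assessment (1.4);
- an external data monitoring committee (7.4, 8.7).

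These lower the risk but do not settle the wording. The ISF holds detailed handling instructions and may already do so.

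**Conclusion.** Wrong as written; minor, on patient-safety grounds. One phrase in operative dosing text presupposes further dosing after an anaphylactic reaction, against a stop rule in the same section that most of the protocol supports. The practical reach is a drug-suspected reaction graded 2 on row A1 that also meets Appendix 10.5. The size cannot be put in numbers, because the documents give no frequency of such reactions and no indication of how often a site would re-dose.

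Three stronger readings are not supported.

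- A reader might infer that the protocol directs re-dosing after anaphylaxis. It does not; the sentence is conditional.
- A reader might take the number of scheduled doses left as the size of the problem. Suppose the last parent-trial visit (18 May 2020) was the latest roll-over visit. Adding 7 days of screening, 84 of re-induction and 7 of waiting for the endoscopy result gives 24 August 2020, which is 637 days, or 91 weeks, before version 8.0 (23 May 2022). A reaction at the next four-weekly visit, week 92, leaves at most (336 − 92)/4 = 61 doses. That is a ceiling on scheduled dosing and says nothing about risk.
- A reader might conclude that a mandatory stop is needed. The present rule is advisory, and making it mandatory would be a substantive change that this inconsistency does not require.

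The verdict assumes that the ISF does not already resolve the point and that the unreproduced RCTC rows do not force a higher grade in the example.

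**What to change.** In section 4.2.1:

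1. Delete *or anaphylactic* from the prophylaxis sentence, and limit it to mild-to-moderate infusion or hypersensitivity reactions that do not meet Appendix 10.5.
2. Add to both steroid sentences, the treatment one and the prophylaxis one, a pointer such as: for anaphylactic reactions see the discontinuation rule below.
3. Keep the stop rule's advisory wording. At most, add that it applies regardless of RCTC grade.

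No new procedure, visit or data item is needed. The cost is that the wording has to go through a protocol amendment, with the ethics and authority approvals described in section 8.1, and that the ISF text must match. It can wait for the next amendment.
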